2.3.2. Benefit Assessment

Based on the expected mode of action of INCB054707, participants randomly assigned to 1 of the 3 active treatment groups may experience clinically meaningful improvements in their vitiligo lesions during the placebo-controlled (24 weeks) period, and all participants will be offered drug therapy with 45 mg or 75 mg during the extension period (28 weeks).

Vitiligo is characterized by a progressive loss of functional melanocytes and associated with auditory abnormalities, including SNHL, with a prevalence ranging from 4.0% to 68.8% when compared with healthy controls ([de Jong et al 2017](#)). During embryogenesis, precursor melanocyte cells (melanoblasts) migrate to the dermis and also to the base of the cochlea, which is responsible for hearing high frequencies. It appears that inner ear melanocytes are very important for cochlear hair cell function and normal hearing ([Rahimi et al 2019](#)). 

Participants will also contribute to the process of developing a novel anti-inflammatory agent expected to induce repigmentation in vitiligo, a disease with high unmet need and that is severely debilitating to participants' psychosocial well-being.

2.3.3. Benefit-Risk Conclusion

Currently, there are no approved drug therapies for vitiligo, and treatments are empirical and directed by the available clinical guidelines. There are limited data on the effectiveness and long-term safety of current therapies, including topical or oral corticosteroids and calcineurin inhibitors. Given the psychosocial burden and stigma caused by vitiligo, patients continue to need effective and safe treatments for their disease.

Considering the safety measures initiated to minimize risk to participants in this study, the potential risks identified in association with INCB054707 are justifiable and appropriately balanced by the anticipated efficacy benefits expected to be afforded to participants.

3. OBJECTIVES AND ENDPOINTS

[Table 6](#) presents the objectives and endpoints.

Table 6: Objectives and Endpoints

Objectives	Endpoints
Primary	
To determine the efficacy of INCB054707.	
Percent change from baseline in Total Vitiligo Area Scoring Index (T-VASI) at Week 24.
Key Secondary	
To further determine the efficacy of INCB054707.	
Proportion of participants achieving T-VASI50 at Week 24. T-VASI50 is defined as 50% or greater reduction in the Total Vitiligo Area Scoring Index.
Secondary	
To evaluate the safety and tolerability of INCB054707.	
Frequency and severity of AEs, including the results of physical examinations, vital signs, evaluation of clinical laboratory studies, and ECGs.

Table 6: Objectives and Endpoints (Continued)

Objectives	Endpoints

Table 6: Objectives and Endpoints (Continued)

Objectives	Endpoints

Table 6: Objectives and Endpoints (Continued)

4. STUDY DESIGN

4.1. Overall Design

This is a Phase 2, multicenter, randomized, parallel-group, placebo-controlled, double-blind, dose-ranging study to evaluate the efficacy and safety of INCB054707 (15, 45, and 75 mg QD) over a 24-week treatment period followed by a 28-week double-blind extension period (INCB054707 45 mg and 75 mg QD), a 4-week safety follow-up period [REDACTED] [REDACTED]. The study will enroll approximately 160 men and women aged 18 to 75 years with nonsegmental vitiligo. [Figure 1](#) presents the study design schema, and [Table 3](#) and [Table 4](#) present the SoA for the placebo-controlled and extension periods, respectively.

Participants will be screened for up to 32 days before the first dose of study drug. Key entry criteria for participants are diagnosis of nonsegmental vitiligo, with depigmented areas including T-BSA \geq 8%, T-VASI \geq 8, F-BSA \geq 0.5%, and F-VASI \geq 0.5. Screening will include assessments described in [Table 3](#).

Participants who meet all the study entry criteria and none of the exclusion criteria will return to the study site on Day 1 of dosing and be randomized in a 1:1:1:1 ratio to 1 of 4 treatment groups (placebo or INCB054707 15, 45, or 75 mg QD). Participant randomization will be stratified based on total BSA involvement, with 2 strata: 8% to 20% and $>$ 20%.

Approximately 160 participants will take oral study drug (placebo, 15 mg, 45 mg, or 75 mg) QD in a blinded manner for 24 weeks. Participants who complete the Week 24 visit will enter the 28-week double-blind extension period with 45 mg QD (for participants who received 45 mg during the placebo-controlled period) or 75 mg (for participants who received placebo, 15 mg, or 75 mg during the placebo-controlled period), with a 4-week safety follow-up period after the last dose of study drug [REDACTED].

The external DSMB will review safety data throughout the study and may provide recommendations regarding changes in the study conduct (see Section [5.6](#)).

Participants will be assessed for safety and tolerability by monitoring the frequency and severity of AEs and performing physical examinations, ECGs, vital signs measurements, and clinical laboratory assessments at various timepoints during the study.

[REDACTED]
[REDACTED]
[REDACTED]

The COVID-19 global pandemic may present challenges to the normal conduct of this study, requiring the outline of potential mitigation strategies described in [Appendix E](#).

4.2. Overall Study Duration

The study begins when the first participant signs the study ICF. The end of the study is defined as the date of the last visit of the last participant in the study or the last scheduled procedure shown in the SoA (see [Table 3](#) and [Table 4](#)) for the last participant in the study globally.

It is estimated that an individual will participate for approximately 19 months, including up to 32 days for screening, continuous treatment for 52 weeks (including placebo-controlled and extension periods, as long as participants are receiving benefit and have not met any criteria for study withdrawal), [REDACTED]

A participant is considered to have completed the study if he/she has completed both the placebo-controlled and the extension periods of the study, including the Week 56 safety follow-up (EOS) visit (see [Table 3](#) and [Table 4](#)). A study is considered completed when the last participant's last visit has occurred.

4.3. Study Termination

The investigator retains the right to terminate study participation at any time, according to the terms specified in the study contract. The investigator is to notify the IRB/IEC of the study's completion or early termination in writing, send a copy of the notification to the sponsor or sponsor's designee, and retain 1 copy for the site study regulatory file.

The sponsor may terminate the study electively if, for example, required by regulatory decision or upon advice of the DSMB (see Section [5.6](#)). If the study is terminated prematurely, the sponsor will notify the investigators, the IRBs and IECs, and the regulatory bodies of the decision and reason for termination of the study.

5. STUDY POPULATION

Deviations from eligibility criteria are not allowed because they can potentially jeopardize the scientific integrity of the study, regulatory acceptability, and/or participant safety. Therefore, adherence to the criteria as specified in the Protocol is essential. Prospective approval of Protocol deviations to recruitment and enrollment criteria, also known as Protocol waivers or exemptions, are not permitted.

5.1. Inclusion Criteria

Participants are eligible to be included in the study only if all of the following criteria apply:

1. Ability to comprehend and willingness to sign an ICF.
2. Men and women aged 18 to 75 years at the time of consent.
3. Clinical diagnosis of nonsegmental vitiligo, with depigmented areas including:
 - a. T-BSA \geq 8%, and
 - b. T-VASI \geq 8, and
 - c. F-BSA \geq 0.5%, and
 - d. F-VASI \geq 0.5.
4. Removed during Protocol Amendment 1.
5. Agreement to discontinue all agents and procedures used to treat vitiligo from screening through the final safety follow-up visit.

6. Agreement to use contraception, as follows (see [Appendix A](#)):

- a. Male participants and female participants of childbearing potential must agree to take appropriate precautions to avoid pregnancy (with at least 99% certainty) from screening through 90 days after the last dose of study drug.
- b. Male participants must refrain from donating sperm during this period. Female participants must refrain from donating oocytes during this period.
- c. Permitted methods that are at least 99% effective in preventing pregnancy should be communicated to the participant and his/her understanding confirmed.

Note: This criterion does not apply to women of nonchildbearing potential (ie, surgically sterile with a hysterectomy and/or bilateral oophorectomy OR postmenopausal, defined as amenorrhea at least 12 months before screening, confirmed by FSH levels at screening).

5.2. Exclusion Criteria

Participants are excluded from the study if any of the following criteria apply:

1. Inability or unwillingness of the participant to sign the ICF.
2. Other forms of vitiligo (eg, segmental) or other skin depigmentation disorders (eg, piebaldism, pityriasis alba, leprosy, postinflammatory hypopigmentation, progressive macule hypomelanosis, nevus anemicus, chemical leukoderma, and tinea versicolor).
3. Uncontrolled thyroid function at screening as determined by the investigator.

Note: If the participant has a history of thyroid disease and is on treatment, the participant must be on a stable thyroid regimen for at least 3 months prior to Day 1.
4. Use of laser or light-based treatment (phototherapy), including tanning beds, within 8 weeks prior to Day 1.
5. Use of dihydroxyacetone (generally present in self-tanning products) within 4 weeks prior to Day 1.
6. Current or past use of the depigmenting agent monobenzyl ether of hydroquinone, including Benoquin® (monobenzene).
7. History of melanocyte-keratinocyte transplantation procedure (MKTP) or other surgical treatment for vitiligo.
8. Spontaneous and significant repigmentation within 6 months prior to screening (eg, repigmentation without any treatment, and significant in amount as determined by the investigator).
9. Women who are pregnant, considering pregnancy, or breastfeeding.

10. Concurrent conditions or history of other diseases, as follows:

- a. Thrombocytopenia, coagulopathy, platelet dysfunction, or history of thrombotic events.
- b. Any clinically significant medical condition other than vitiligo, as determined by the investigator, that is not adequately controlled with appropriate treatment **OR** may interfere with the course, severity, or assessments of this study.
- c. Any other active skin disease or condition that may interfere with the course, severity, or assessments of this study.
- d. Any bacterial, fungal, or viral infection that, based on the investigator's clinical assessment, makes the participant an unsuitable candidate for the study.
- e. Current herpes zoster infection, a history of disseminated herpes simplex, or a history of herpes zoster.
- f. History of malignancy, including melanoma, lymphoma, and leukemia within 5 years before Day 1, other than a successfully treated nonmetastatic cutaneous squamous cell carcinoma, basal cell carcinoma, or localized carcinoma in situ of the cervix.
- g. Albinism.

11. History of treatment failure for vitiligo, or any other inflammatory condition, with any systemic or topical JAK or TYK2 inhibitor (eg, ruxolitinib, tofacitinib, baricitinib, filgotinib, lesartanib, pacritinib, abrocitinib, breycopitinib).

12. Current use of anticoagulants or medications known to cause thrombocytopenia.

13. Receipt of medications or investigational drugs within the following interval before Day 1 (first administration of study drug):

- a. < 12 weeks or 5 half-lives (if known), whichever is longer, for any topical or systemic JAK or TYK2 inhibitor.
- b. < 12 weeks or 5 half-lives (if known), whichever is longer, for any investigational or experimental treatments.
- c. < 12 weeks or 5 half-lives (if known), whichever is longer, for systemic immunosuppressive or immunomodulating biologic drugs (eg, adalimumab, etanercept, infliximab, golimumab, certolizumab, ustekinumab, secukinumab, brodalumab, ixekizumab, risankizumab, guselkumab, bimekizumab, iscalimab, bermekimab, rituximab, anakinra).
- d. < 6 weeks for live vaccine, or planning to receive live vaccine during the course of the study or within 6 weeks after the last dose of study drug.
- e. < 4 weeks for systemic immunosuppressive or immunomodulating small-molecule drugs (eg, oral or injectable corticosteroids, methotrexate, cyclosporine, dapsone, azathioprine).

Note 1: Use of corticosteroid inhalers and intranasal sprays is allowed.

Note 2: Use of oral corticosteroids for nondermatologic conditions (eg, asthma exacerbation, bronchitis) is allowed for no longer than 7 days, if deemed acceptable by the investigator and the sponsor.

Note 3: Use of topical corticosteroids for dermatologic disease other than vitiligo (eg, atopic dermatitis or psoriasis) is allowed for areas not being treated for vitiligo. The total BSA involvement for other dermatologic diseases, outside of the areas treated for vitiligo, must not exceed 10%.

- f. < 3 weeks for any oral or topical PDE-4 inhibitor (eg, apremilast, crisaborole).
- g. < 2 weeks for any topical drug applied onto vitiligo lesions.
- h. < 2 weeks for any OTC therapies used for vitiligo treatment.
- i. < 2 weeks or 5 half-lives (if known), whichever is longer, for strong and moderate systemic CYP3A4 inhibitors and strong systemic CYP3A4 inducers. Examples include but are not limited to the following (see [Appendix B](#) for details): erythromycin, rifampicin/rifampin, ciprofloxacin, some azole antifungals (eg, ketoconazole, fluconazole), nefazodone, St John's wort, diltiazem, mibepradil, verapamil, grapefruit/grapefruit juice, and Seville oranges.
- j. < 1 week for antiplatelet drugs.

Note: Low-dose acetylsalicylic acid (≤ 100 mg QD) is permitted for the purpose of cardiovascular prophylaxis at the discretion of the investigator.

14. Laboratory values at screening defined in [Table 7](#).

Table 7: Exclusionary Laboratory Values

Laboratory Parameter		Exclusion Criterion
Hematology		
a	Platelets	$< 150 \times 10^9/L$
b	Hemoglobin	$< 10 \text{ g/L}$
c	ANC	$< 1.5 \times 10^9/L$
d	WBC	$\leq 3.0 \times 10^9/L$
Hepatic		
e	ALT	$\geq 2 \times \text{ULN}$
f	AST	$\geq 2 \times \text{ULN}$
g	Total bilirubin	$\geq 1.5 \times \text{ULN}$ (Note: unless clinical diagnosis of Gilbert's syndrome)
h	Alkaline phosphatase	$\geq 2 \times \text{ULN}$
Renal		
j	Serum creatinine	$> 1.25 \times \text{ULN}$
Coagulation		
l	PT	$> \text{ULN}$
m	INR	$> \text{ULN}$

15. Evidence of HBV or HCV infection or risk of reactivation. Participants cannot be positive for hepatitis B surface antigen, anti-hepatitis B core antibody, or HCV antibody; participants also cannot be positive for HBV DNA or HCV RNA in case these reflexive assessments are required to be performed.

Note: Participants with no prior history of HBV infection who have been vaccinated against HBV and who have a positive antibody (hepatitis B surface antibody) against HBsAg as the only evidence of prior exposure may participate in the study.

16. Known HIV infection.
17. Evidence of active or latent or inadequately treated infection with *Mycobacterium tuberculosis* (ie, TB) as defined by the following:
 - a. A positive QFT-GIT or positive Mantoux/PPD tuberculin skin test performed at or within the 12 weeks prior to Day 1 is exclusionary; a negative test is required for eligibility unless other criteria as described here are applicable. It is recommended that participants with a history of Bacille Calmette-Guérin vaccination be tested with the QFT-GIT, because the Mantoux/PPD tuberculin skin test may be positive due to vaccination. A QFT-GIT or Mantoux/PPD tuberculin skin test is not required if the participant has previously received a documented adequate course of therapy for either latent or active TB infection.
 - b. A history of either untreated or inadequately treated latent or active TB infection.
 - c. If a participant has previously received an adequate course of therapy for either latent TB infection (9 months of isoniazid in a locale where rates of primary multidrug TB resistance are < 5% or an acceptable alternative regimen) or active TB infection (an acceptable multidrug regimen), neither a QFT-GIT nor a Mantoux/PPD tuberculin skin test is needed, but a chest x-ray(s) or other appropriate diagnostic image, performed within 3 months of Day 1, is required. To be considered eligible for the study, the x-ray(s) must be negative for active TB infection as determined by a qualified radiologist. Documentation of adequate treatment for TB and negative chest x-ray(s) results must be obtained prior to Day 1.
 - d. A participant who is currently being treated for active TB infection is to be excluded.
18. Known hypersensitivity or severe reaction to INCB054707 or excipients of INCB054707 (refer to [IB](#)).
19. Inability or unlikeness of the participant to comply with the dose schedule and study evaluations, in the opinion of the investigator.
20. Any condition that would, in the investigator's judgment, interfere with full participation in the study, including administration of study drug and attending required study visits; pose a significant risk to the participant; or interfere with interpretation of study data.

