2.3.1. Clinical Studies

Single doses of INCB054707 up to 405 mg and multiple doses of INCB054707 up to 120 mg QD for up to 10 days have been evaluated in 2 placebo-controlled studies in healthy participants. The most common TEAEs were mild to moderate headache in 31% of participants who received INCB054707 in the multiple-dose study; the events were not dose-dependent and resolved spontaneously following discontinuation of INCB054707. Furthermore, decreases in platelet counts were observed among participants treated with INCB054707 at doses \geq 60 mg QD. The magnitude of the decrease was larger for participants treated with 120 mg QD compared with those who received 60 mg QD, suggesting a dose-related trend. Of note, for the participants with a treatment-emergent decrease in platelet counts, the platelet counts remained within the normal range.

In 2 clinical studies in participants with HS, INCB 54707-202 (15 mg only) and INCB 54707-203 (placebo and 30, 60, and 90 mg), QD doses of study drug were administered for up to 8 weeks. Transient and asymptomatic thrombocytopenia was observed in 4 of 8 participants who received INCB054707 90 mg QD after 4 weeks of exposure, which led to dose interruption for a maximum of 2 weeks, and resolved without medical intervention. All participants returned to their normal dosing schedule after dose interruption and completed the study without clinical sequelae or re-emergence of thrombocytopenia. Platelet count decreases have been transient and stabilize over time, as observed in studies with other JAK1 inhibitors for treatment of other dermatologic indications, such as abrocitinib in atopic dermatitis ([Gooderham et al 2019](#)) and itacitinib in plaque psoriasis ([Bissonnette et al 2016](#)). Thrombocytopenia TEAEs were asymptomatic and judged as treatment-related. Hemoglobin levels remained within normal limits and were mostly unchanged during the study, while neutrophil counts showed a mild dose-dependent decrease within normal limits. Across the 2 studies, the most common TEAE was fatigue, observed in 6 of the 36 participants (17%). Mild-to-moderate headache was observed in 11% (4 of 36) of the participants exposed to INCB054707 and in 22% (2 of 9) of the participants exposed to placebo. No serious or fatal TEAEs were reported in the studies; more details are provided in the [IB](#).

[figure not shown]

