8.1.2. Screening Procedures

Screening is the interval between signing the ICF and the day the participant is randomized in the study (Day 1). Screening may not exceed 32 days. Assessments that are required to demonstrate eligibility may be performed over the course of 1 or more days during the screening process.

Results from the screening visit evaluations will be reviewed to confirm eligibility before randomization or the administration of study drug. Tests with results that fail eligibility requirements may be repeated once during screening if the investigator believes the results to be in error. For screening assessments that are repeated, the most recent available result before randomization will be used to determine eligibility.

See Sections [5.4](#) and [5.5](#) for information regarding screen failures and replacement of participants, respectively.

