8.3.5. Laboratory Assessments

See [Table 13](#) for the list of clinical laboratory tests to be performed and [Table 3](#) and [Table 4](#) for the laboratory assessment visit schedule. A central laboratory will perform all clinical laboratory assessments for safety (ie, blood chemistries, hematology assessments, coagulation tests, endocrine function, and urinalysis), [REDACTED]. [REDACTED]

[REDACTED] Additional testing may be required by the investigator or sponsor based on emerging safety data. All Protocol-required laboratory assessments must be conducted in accordance with the Laboratory Manual and [Table 3](#) and [Table 4](#).

If visits at Week 2, Week 6, Week 26, and Week 30 are scheduled as remote, blood collection will be conducted remotely (eg, participant's home or workplace); otherwise blood will be collected during in-clinic visit (see [Table 3](#) and [Table 4](#)). At-home sampling for additional laboratory assessments may also be conducted; see [Appendix E](#) for COVID-19-related guidance.

Information regarding collection, processing, and shipping of samples for laboratory assessment is provided in the Laboratory Manual.

Clinically significant abnormal laboratory findings are those that are not associated with the underlying disease, unless judged by the investigator to be more severe than expected for the participant's condition. All laboratory tests with values considered clinically significantly abnormal during participation in the study (including any unscheduled testing within the 24-week follow-up period) should be repeated until the values return to normal or baseline or are no longer considered clinically significant by the investigator or medical monitor.

If screening laboratory assessments are performed more than 32 days before Day 1, then the tests must be repeated and eligibility confirmed before study drug administration on Day 1.

Laboratory sample collection on Day 1 must be performed before study drug administration.

See Section 9.1 for information regarding laboratory abnormalities that should be recorded as an AE in the eCRF.

Table 13: Required Laboratory Analytes

Blood Chemistries	Hematology	Urinalysis	Serology / Infection	Pregnancy Testing

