10.2. Populations for Analysis

[figure not shown]
The populations for analysis are provided in [Table 16](#).

Table 16: Populations for Analysis

Population	Description
ITT	The ITT population includes all randomized participants. Treatment groups for this population will be defined according to the treatment assignment at randomization.
Safety	The safety population includes all participants who received at least 1 dose of study drug. Treatment groups for this population will be determined according to the actual treatment the participant received on Day 1.

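### The screening haemoglobin limit in Table 7 reads < 10 g/L, which is 1 g/dL, so the row cannot exclude anyone

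*Protocol*

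**What the plan says.** Criterion 14 in Protocol Section 5.2 makes the limits in Table 7 binding at screening. Row b, under haematology, reads "Hemoglobin $< 10 \text{ g/L". Section 5 rules out waivers and states that "adherence to the criteria as specified in the Protocol is essential". Section 8.1.2 describes how the criteria are applied: "Results from the screening visit evaluations will be reviewed to confirm eligibility before randomization or the administration of study drug". Section 8.3.5 adds that "A central laboratory will perform all clinical laboratory assessments for safety".

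Two other exclusion criteria could cover anaemia without naming it:

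- Criterion 10b: "Any clinically significant medical condition other than vitiligo, as determined by the investigator, that is not adequately controlled with appropriate treatment". It also covers conditions that may interfere with the study.
- Criterion 20 includes conditions that would "pose a significant risk to the participant; or interfere with interpretation of study data".

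On earlier experience with the drug, Section 2.3.1 reports from the hidradenitis suppurativa studies: "Hemoglobin levels remained within normal limits and were mostly unchanged during the study".

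**The concern.** A limit of 10 g/L lies far below any haemoglobin that a person walking into a clinic would have. A criterion set there does nothing, although the sponsor evidently meant haemoglobin to be one of the numeric screening limits. Since the criteria must be followed as written, a site has two options. It can apply the cell literally, and then has no haemoglobin limit. Or it can apply some other number, and then departs from the written criterion. Sites may differ, and the eligibility record would not show which limit was used.

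What is at stake is participant safety and a clear eligibility record. A participant with marked anaemia could be randomised to up to 52 weeks of treatment unless the investigator chose to exclude on judgement. The reassuring haemoglobin data in Section 2.3.1 come from dosing of up to 8 weeks.

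**Working it through.** The row is a stated limit, not a derived figure, so there is no calculation in the plan to reproduce. The check is a unit conversion followed by a search for another limit.

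**Inputs**

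- Printed limit: < 10 g/L (Protocol Table 7, row b).
- Conversion: 1 L = 10 dL.
- Assumption, not in the documents: outpatient haemoglobin of 60 to 180 g/L. The range is deliberately wide.
- Assumption, not in the documents: mean corpuscular haemoglobin concentration (MCHC) of 300 to 360 g/L, used only as a plausibility check.

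**Conversion**

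- As printed: 10 g/L ÷ 10 dL/L = 1.0 g/dL.
- Same number read in g/dL: 10 g/dL × 10 dL/L = 100 g/L.
- Ratio of the two readings: 100 ÷ 10 = 10. Difference: 100 − 10 = 90 g/L.

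The second reading is shown only to size the ambiguity. It is not offered as the correct limit.

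**Would the row exclude anyone?**

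- Lowest assumed value over the limit: 60 ÷ 10 = 6.
- Highest assumed value over the limit: 180 ÷ 10 = 18.
- Every assumed result is 6 to 18 times the limit, so the row excludes 0 participants.
- Implied haematocrit at 10 g/L is haemoglobin ÷ MCHC: 10 ÷ 360 = 2.8% to 10 ÷ 300 = 3.3%. That is not a plausible value in an ambulatory person.

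**Is there another numeric limit?**

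| Place | What it gives on haemoglobin |
|---|---|
| Protocol Section 5.2, criteria 10b and 20 | Investigator judgement, no number |
| Protocol Section 8.3.5, Table 13 | Listed as an analyte only |
| Protocol Section 2.3.1 | Description of earlier studies, no value or unit |
| Protocol Appendix F, Amendment 1 | Records a Table 7 change for bilirubin, none for haemoglobin |
| Protocol Tables 9 and 10 (not visible) | Dose interruption and discontinuation, not eligibility |
| SAP Table 6 (not visible) | Flags for potentially important laboratory values, not eligibility |

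Nothing that can be seen supplies a working screening limit.

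**The case against.** The strongest objection is that the error may lie in the reading of the page and not in the protocol. The point turns on one letter in one table cell, in text read from PDF by a program, and there are letter-level faults nearby. Table 7's row letters skip i and k. Drug names in criterion 11 are spelled differently from the same list in Section 6.6.3. Table 13 assigns pregnancy tests to women of nonchildbearing potential, whereas Tables 3 and 4 and Section 8.3.5.1 assign them to women of childbearing potential. This risk stands. It is why the source page must be checked first and why confidence is only moderate. Nothing in row b itself shows a misreading, however, and the neighbouring haematology limits read coherently.

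A second objection is that the consequence is slight. An impossible unit would probably be queried. Criteria 10b and 20 remain. Tables 3 and 4 schedule haematology at screening, at baseline and throughout treatment, and Section 8.6 requires repeat testing of potential clinically significant abnormalities. This limits the harm, but it does not replace a common entry limit. Monitoring also begins to help only after the participant has been enrolled.

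A third is that the Laboratory Manual, which is not available here, may carry the working limit. That is possible, so differences between sites are a risk and not an established fact. The SAP's rule on SI units (Section 8.3.2) does not settle the matter, because it governs the reporting of results and not eligibility decisions.

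Finally, listing participants against a limit corrected later would test them against something that was not the written criterion when they entered. That is fair as to status: such a listing is descriptive and does not by itself make anyone a protocol deviation.

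**Conclusion.** The concern holds. As it reads, the haemoglobin row is inoperative: the limit equals 1.0 g/dL, and the two readings of the cell differ ten-fold (90 g/L). Under the assumed outpatient range of 60 to 180 g/L the row excludes nobody. That part rests on general physiology, because the documents give no haemoglobin reference range. Entry with marked anaemia is therefore left to judgement under criteria 10b and 20.

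This is a wrong eligibility threshold with a bearing on safety, so it should be fixed, but its reach is limited. It does not touch alpha, power or the analysis sets: under Protocol Section 10.2, "The ITT population includes all randomized participants". The conclusion depends on the source page matching the text quoted here. If it does not, the point falls.

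**What to change.** 1. Check Table 7 row b against the source page.
2. If it reads as quoted, the sponsor should reconcile the value and the unit and correct the cell. This review does not say which is right.
3. Confirm which limit and unit the sites and the central laboratory applied at screening.
4. List any randomised participants whose screening haemoglobin falls below the corrected limit, as a descriptive safety listing.

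The cost is a one-cell protocol correction, one confirmation from the central laboratory and the sites, and one listing. Design, sample size and analysis do not change.
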